3.1.1. Study Schema

*DLT assessment after 1 cycle (4 weeks)

*DLT = Grade III or higher SAE attributed to treatment

**Patients will have two de-escalation dose levels for (-1 and -2) for all patients based on interim toxicities.

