5.2.1. Route and schedule

Repeat every 28 days

Dose Level	Nivolumab dose	Ibrutinib dose (days 1-28)*
Level 0	240 mg IV q2 weeks	560mg PO
Level -1	240 mg IV q2 weeks	420mg PO

*should be taken at the same time every day

Dose limiting toxicity (DLT) must be treatment-related (possibly, probably, or definitely). To be evaluable for DLT, the subject must have had one dose of Nivolumab and at least 3 weeks of Ibrutinib.

Dose limiting toxicity (DLT) is defined as:

- 1) Grade 4 absolute neutrophil count with fever (>101.4 F) or documented infection;
- 2) Grade 4 thrombocytopenia or Grade 3 thrombocytopenia with bleeding;
- 3) Any grade 3 or greater non-hematologic toxicity excluding alopecia.

DLT will be assessed after 1 cycle (4 weeks).

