5.3.1.4. Dose Modification for Adverse Reactions

The dose of study drug should be modified according to the dose modification guidelines in Table 1 if any of the following toxicities occur:

- Grade 4 ANC (<500/ μ L) for more than 7 days or fibroneutropenia.
- Grade 3 thrombocytopenia (<50,000/ μ L) in the presence of clinically significant bleeding events.
- Grade 4 thrombocytopenia (<25,000/ μ L).
- Grade 3 or 4 nausea, vomiting, or diarrhea if persistent, despite optimal anti-emetic and/or anti-diarrheal therapy.
- Any other Grade 4 or unmanageable Grade 3 toxicity.

For Grade 3 or 4 atrial fibrillation or persistent atrial fibrillation of any grade, consider the risks and benefits of ibrutinib treatment. If clinically indicated, the use of anticoagulants or antiplatelet agents may be considered for the thromboprophylaxis of atrial fibrillation (Section 6.2.4).

Note: After a dose reduction, dose escalation of ibrutinib to a previous higher dose is NOT allowed.

Table 1. Ibrutinib Dose Modifications

Occurrence	Action to be Taken
First	Withhold study drug until recovery to Grade ≤ 1 or baseline; may restart at original dose level
Second	Withhold study drug until recovery to Grade ≤ 1 or baseline; may restart at 1 dose level lower (ie, 280 mg/day for 420 mg/day dose; 420 mg/day for 560 mg /day dose)
Third	Withhold study drug until recovery to Grade ≤ 1 or baseline; may restart at 1 dose level lower (ie, 140 mg/day for 420 mg/day dose; 280 mg/day for 560 mg /day dose)
Fourth	Discontinue study drug

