9.2. Withdrawal from Study Treatment

Study treatment will be discontinued in the event of any of the following events:

1. Unacceptable toxicity
2. Treatment failure or no evidence of clinical benefit per investigator assessment
3. An intercurrent illness or adverse event that prevents further ibrutinib administration.

4. Withdrawal of consent for treatment by subject
5. Investigator decision (such as chronic noncompliance, significant protocol deviation, or best interest of the subject)
6. Study termination by Pharmacyclics or study sponsor
7. Subject becomes pregnant
8. Nivolumab is held for greater than 42 days (the subject can stay on study with Ibrutinib only)
9. Ibrutinib is held for greater than 4 weeks. If Ibrutinib therapy is held for greater than 4 weeks, then the subject must discontinue from the nivolumab as well

All subjects, regardless of reason for discontinuation of study treatment will undergo an End of Treatment Visit and be followed for treatment failure and survival.

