10.4. Analysis Populations

10.4.1. Safety Population

The safety population will include all patients who receive at least one dose of either study drug. A baseline measurement and at least one laboratory, vital sign, or other safety-related measurement obtained after at least one dose of study medication may be required for inclusion in analyses of a specific safety parameter.

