10.5. Statistical Methods

Primary endpoint: Progression-free survival (PFS) as the number of months from baseline to death or progression, defined in Appendix 4. The duration of PFS will be summarized descriptively using Kaplan-Meier survival plots and life tables. The number and proportion with PFS of 6 months or more will be reported, adjusting for censoring using the life-table approach. If the number with PFS at least six months is 15 or more out of 25 evaluable patients, this will constitute evidence supporting an improvement over historic PFS rates.

Secondary endpoints: RECIST response will be calculated as in Appendix 4, and will be summarized by the number and percentage of patients, accompanied by 2-sided exact 95% confidence intervals. Overall survival will be summarized descriptively by Kaplan-Meier curves and life table estimates, as for PFS. Number and type of adverse events will be summarized descriptively by system organ class affected and by grade of event, overall and by dose. Vital signs and laboratory test results will be summarized descriptively (mean, SD, range) overall and by dose.

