12.4. Data and Safety Monitoring

In addition to the requirements for adverse event reporting as outlined in Section 11, this protocol is also subject to the UC Davis Cancer Center's (UCDCC) Data and Safety Monitoring Plan. The UCDCC is committed to pursuing high-quality patient-oriented clinical research and has established mechanisms to ensure both scientific rigor and patient safety in the conduct of clinical research studies. The UCDCC relies on a multi-tiered committee system that reviews and monitors all cancer clinical trials and ensures the safety of its participants, in compliance with institutional and federal requirements on adverse event (AE) reporting, verification of data

accuracy, and adherence to protocol eligibility requirements, treatment guidelines, and related matters. The Scientific Review Committee (SRC) assumes overall oversight of cancer studies, with assistance and input from two independent, but interacting, committees: the Quality Assurance Committee and the Data Safety Monitoring Committee. A multi-level review system strengthens the ability of the UCDCC to fulfill its mission in conducting high quality clinical cancer research.

As per University of California Davis Cancer Center (UCDCC) Office of Clinical Research (OCR) SOP AM 506: Protocol Specific Meetings, the principal investigator (PI) and clinical research coordinator (CRC) meet at least monthly for ongoing study information, to discuss patient data and adverse events and to determine if dose escalation is warranted, when applicable.

According to the UCDCC Data and Safety Monitoring Plan (DSMP), any new serious adverse events related to the drugs being used on this trial are reviewed monthly by the UCDCC Data and Safety Monitoring Committee (DSMC) and any applicable changes to the study are recommended to the PI, if necessary.

The UCDCC Scientific Review Committee (SRC) determines if a UCDCC Data and Safety Monitoring Board (DSMB) is required. If required, the DSMC will appoint a DSMB. The DSMB is responsible for reviewing study accrual logs, adverse event information and dose escalation meeting minutes (where applicable) to ensure subject safety and compliance with protocol defined guidelines.

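### The DLT-evaluability rule has no exception for patients who have a DLT, so an early DLT that stops ibrutinib drops out of the DLT count

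*Combined protocol and SAP*

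**What the plan says.** Section 5.2.1 sets the counting rule: "To be evaluable for DLT, the subject must have had one dose of Nivolumab and at least 3 weeks of Ibrutinib". The same section places the DLT assessment after one 28-day cycle. It limits DLTs to treatment-related events and lists three criteria: grade 4 neutropenia with fever or infection, grade 4 thrombocytopenia (or grade 3 with bleeding), and any non-hematologic toxicity of grade 3 or above except alopecia. The note to the schema in section 3.1.1 gives a different definition: "DLT = Grade III or higher SAE attributed to treatment".

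Ibrutinib exposure can be cut short by toxicity in two ways:

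- Section 5.3.1.4 lists triggers for modifying ibrutinib, ending with "Any other Grade 4 or unmanageable Grade 3 toxicity". Table 1 withholds the drug until recovery to grade 1 or baseline, with no fixed duration.
- Section 9.2 ends treatment for unacceptable toxicity and for "An intercurrent illness or adverse event that prevents further ibrutinib administration".

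The safety analysis uses a wider set: "The safety population will include all patients who receive at least one dose of either study drug" (section 10.4.1). The schema notes tie de-escalation to toxicities seen in the interim. The readable text gives no cohort size, no numerical threshold and no replacement rule.

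**The concern.** A minimum-exposure requirement exists so that a patient who took little drug and had no toxicity is not counted as having tolerated the dose. It should not apply to a patient who has already had the event being counted. As written, it applies to everyone. A patient with a serious early reaction who stops ibrutinib, or who dies of it, fails the exposure test because of the DLT.

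The loss therefore depends on the outcome, and it falls on the events severe or early enough to interrupt ibrutinib. At stake is the cycle 1 DLT count at each dose level, in a phase Ib/II study whose primary objective includes feasibility and whose secondary objective is safety. Two sites are planned, and each could apply the sentence differently.

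**Working it through.** The plan states no DLT rate, so there is no figure to reproduce. The check has two parts: a reading of the rule, and an illustration of its effect under stated assumptions.

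**Reading the rule**

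1. Section 5.2.1 makes the requirement unconditional. Sections 3.1.1 (readable notes), 5.3.1.4, 9.2, 10.1, 10.4, 10.5 and 12.4 contain no exception for a patient with a DLT.
2. DLT criteria and ibrutinib-hold triggers overlap: grade 4 thrombocytopenia, grade 3 thrombocytopenia with bleeding, and grade 4 or unmanageable grade 3 toxicity generally.
3. Example: a related grade 4 non-hematologic event occurs on day 8 and ibrutinib is not restarted. Exposure is at most 8 days, against the required 21. The event meets the DLT definition, but the patient is not DLT-evaluable.
4. Not every DLT is lost. The DLT definition is wider than the hold triggers, and a first event may restart at the original dose. A DLT after day 21 of uninterrupted dosing still counts.
5. The text does not say whether the 3 weeks must fall within cycle 1. If they must, the margin is 28 − 21 = 7 days, and missing more than 7 days loses evaluability.

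**Size, under assumptions**

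These three quantities are not in the documents:

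- *d*: true probability of a cycle 1 DLT
- *e*: share of DLT patients left with less than 3 weeks of ibrutinib
- *f*: share of patients without a DLT who miss the minimum

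Among evaluable patients,

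observed rate = d(1 − e) / [d(1 − e) + (1 − d)(1 − f)].

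Worked example with d = 0.33, e = 0.50, f = 0: 0.165 / (0.165 + 0.67) = 0.165 / 0.835 = 0.198. With f = 0.10: 0.165 / (0.165 + 0.603) = 0.165 / 0.768 = 0.215.

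| d | f | e = 10% | e = 25% | e = 50% | e = 75% |
|---|---|---|---|---|---|
| 0.33 | 0 | 0.307 | 0.270 | 0.198 | 0.110 |
| 0.33 | 0.10 | 0.330 | 0.291 | 0.215 | 0.120 |
| 0.20 | 0 | 0.184 | 0.158 | 0.111 | 0.059 |

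In odds form, the observed odds equal the true odds multiplied by (1 − e)/(1 − f). The bias is downward only when e exceeds f, and it vanishes when e = f, as in the first cell of the second row. Under the corrected rule e = 0, so no DLT is lost.

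**The case against.** The strongest reply is that the decisive text may be in the schema. Section 5.2 refers the reader there, and only its footnotes are readable. Cohort sizes, a threshold or an exception may be in the drawing. This stands as a limit on the finding. If an exception is there, section 5.2.1 contradicts it and still needs correcting.

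The second reply is that the DLT count has no visible consequence. It is not among the endpoints in section 10.2, and the schema notes speak of toxicities in general, so an early severe event could prompt de-escalation whether or not the patient is evaluable. The event also remains in the safety population and in the adverse-event summaries "by grade of event, overall and by dose". Under section 12.4, new serious events related to the study drugs "are reviewed monthly by the UCDCC Data and Safety Monitoring Committee". All of this is correct. It confines the harm to the DLT count and means that no wrong dose decision has been shown. It does not repair a count made under the written rule.

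The third reply is that *e* may be small. Evaluability needs only one nivolumab dose, which is given on day 1, and Tables 2 to 6 hold or stop nivolumab without mentioning ibrutinib. An immune-related DLT managed that way leaves the patient evaluable unless ibrutinib is also held. This makes the right-hand columns of the table less likely but leaves the mechanism in place.

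Finally, the team may intend to count such patients. The text does not say so.

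**Conclusion.** The concern holds. Section 5.2.1 states a rule that, followed as written, removes from the DLT count any patient whose DLT leaves less than 3 weeks of ibrutinib. This is an error in the stated rule, not a missing detail. It should be fixed.

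The size cannot be derived from the documents. For an assumed true rate of 33%, the observed rate ranges from unchanged (equal loss in both groups), through 31% (10% of DLT patients lost, no other loss), to 11% (75% lost, no other loss). The conclusion about direction requires that DLT patients miss the minimum more often than other patients. The conclusion about the text rests on the readable document, without the schema drawing. How the DLT count enters de-escalation is not readable, so no effect on dose decisions is claimed.

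**What to change.** Restate the evaluability sentence in section 5.2.1 as a counting rule:

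1. Any treated patient with a DLT in cycle 1 is DLT-evaluable, whatever the exposure.
2. The exposure minimum applies only to patients without a DLT. Those who miss it, for any reason, are non-evaluable.
3. The number in item 2 who missed the minimum because of toxicity is reported separately, so that losses from toxicity short of a DLT stay visible.
4. State whether the 3 weeks of ibrutinib are counted within cycle 1.

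Separately, the DLT definitions in sections 3.1.1 and 5.2.1 differ and must be reconciled, so that a single definition applies to item 1. If the schema drawing contains its own evaluability note, align it with the new wording.

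The cost is a short text change. No new data are collected, and no dose or treatment rule is altered. The reported DLT rate may be higher than under the present wording.

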5.3. Study Medication

5.3.1. Ibrutinib

5.3.1.1. Formulation/Packaging/Storage

Ibrutinib capsules are provided as a hard gelatin capsule containing 140 mg of ibrutinib. All formulation excipients are compendial and are commonly used in oral formulations. Refer to the ibrutinib Investigator's Brochure for a list of excipients.

The ibrutinib capsules will be packaged in opaque high-density polyethylene plastic bottles with labels bearing the appropriate label text as required by governing regulatory agencies. All study drugs will be dispensed in child-resistant packaging.

Refer to the pharmacy manual/site investigational product manual for additional guidance on study drug storage, preparation and handling.

Study drug labels will contain information to meet the applicable regulatory requirements.

5.3.1.2. Dose and Administration

Ibrutinib is administered orally once daily. The capsules are to be taken around the same time each day with 8 ounces (approximately 240 mL) of water. The capsules should be swallowed intact and subjects should not attempt to open capsules or dissolve them in water. The use of strong CYP3A inhibitors/inducers, and grapefruit and Seville oranges should be avoided for the duration of the study (Appendix 3).

If a dose is not taken at the scheduled time, it can be taken as soon as possible on the same day with a return to the normal schedule the following day. The subject should not take extra capsules to make up the missed dose.

The first dose will be delivered in the clinic on Day 1, after which subsequent dosing is typically on an outpatient basis. Ibrutinib will be dispensed to subjects in bottles at each visit. Unused ibrutinib dispensed during previous visits must be returned to the site and drug accountability records (Section 12.8) updated at each visit. Returned capsules must not be redisposed to anyone.

5.3.1.3. Overdose

Any dose of study drug in excess of that specified in this protocol is considered to be an overdose. Signs and symptoms of an overdose that meet any Serious Adverse Event criterion must be reported as a Serious Adverse Event in the appropriate time frame and documented as clinical sequelae to an overdose.

There is no specific experience in the management of ibrutinib overdose in patients. No maximum tolerated dose (MTD) was reached in the Phase 1 study in which subjects received up to 12.5 mg/kg/day (1400 mg/day). Healthy subjects were exposed up to single dose of 1680 mg. One healthy subject experienced reversible Grade 4 hepatic enzyme increases (AST and ALT) after a dose of 1680 mg. Subjects who ingested more than the recommended dosage should be closely monitored and given appropriate supportive treatment.

Refer to Section 11.3 for further information regarding special reporting situations as a result of overdose.

5.3.1.4. Dose Modification for Adverse Reactions

The dose of study drug should be modified according to the dose modification guidelines in Table 1 if any of the following toxicities occur:

- Grade 4 ANC (<500/ μ L) for more than 7 days or fibroneutropenia.
- Grade 3 thrombocytopenia (<50,000/ μ L) in the presence of clinically significant bleeding events.
- Grade 4 thrombocytopenia (<25,000/ μ L).
- Grade 3 or 4 nausea, vomiting, or diarrhea if persistent, despite optimal anti-emetic and/or anti-diarrheal therapy.
- Any other Grade 4 or unmanageable Grade 3 toxicity.

For Grade 3 or 4 atrial fibrillation or persistent atrial fibrillation of any grade, consider the risks and benefits of ibrutinib treatment. If clinically indicated, the use of anticoagulants or antiplatelet agents may be considered for the thromboprophylaxis of atrial fibrillation (Section 6.2.4).

Note: After a dose reduction, dose escalation of ibrutinib to a previous higher dose is NOT allowed.

Table 1. Ibrutinib Dose Modifications

Occurrence	Action to be Taken
First	Withhold study drug until recovery to Grade ≤ 1 or baseline; may restart at original dose level
Second	Withhold study drug until recovery to Grade ≤ 1 or baseline; may restart at 1 dose level lower (ie, 280 mg/day for 420 mg/day dose; 420 mg/day for 560 mg /day dose)
Third	Withhold study drug until recovery to Grade ≤ 1 or baseline; may restart at 1 dose level lower (ie, 140 mg/day for 420 mg/day dose; 280 mg/day for 560 mg /day dose)
Fourth	Discontinue study drug

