4.2. Exclusion Criteria

To be enrolled in the study, potential subjects must meet NONE of the following exclusion criteria:

Concurrent Conditions

1. Cytotoxic chemotherapy \leq 21 days prior to first administration of study treatment and/or monoclonal antibody \leq 4 weeks prior to first administration of study treatment and/or other RCC-directed systemic therapy \leq 2 weeks prior to first administration of study treatment
2. Any known additional malignancy that is progressing or requires active treatment. Exceptions include basal cell carcinoma of the skin, squamous cell carcinoma of the skin, or in situ cervical cancer that has undergone potentially curative therapy.
3. Concurrent systemic immunosuppressant therapy (eg, cyclosporine A, tacrolimus, etc., or chronic administration [>14 days] of >10 mg/day of prednisone) within 28 days of the first dose of study drug.
4. Vaccinated with live, attenuated vaccines within 4 weeks of first dose of study drug.
5. Recent infection requiring systemic treatment that was completed \leq 14 days before the first dose of study drug.
6. Unresolved toxicities from prior anti-cancer therapy, defined as having not resolved to Common Terminology Criteria for Adverse Event (CTCAE, version 4), grade \leq 1, or to the levels dictated in the inclusion/exclusion criteria with the exception of alopecia.
7. Known bleeding disorders (eg, von Willebrand's disease) or hemophilia.
8. History of stroke or intracranial hemorrhage within 6 months prior to enrollment.
9. Known history of human immunodeficiency virus (HIV) or active with hepatitis C virus (HCV) or hepatitis B virus (HBV). *Subjects who are positive for hepatitis B core antibody or hepatitis B surface antigen must have a negative polymerase chain reaction (PCR) result before enrollment. Those who are PCR positive will be excluded.*
10. Any uncontrolled active systemic infection.
11. Major surgery within 4 weeks of first dose of study drug.
12. Any life-threatening illness, known autoimmune disease, medical condition, or organ system dysfunction that, in the investigator's opinion, could compromise the subject's safety or put the study outcomes at undue risk.

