6.4.2. Major Surgical Procedures

For any surgery or invasive procedure requiring sutures or staples for closure, ibrutinib should be held at least 7 days prior to the intervention and should be held at least 7 days after the procedure and restarted at the discretion of the investigator when the surgical site is reasonably healed without serosanguineous drainage or the need for drainage tubes.

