6.4.3. Emergency Procedures

For emergency procedures, ibrutinib should be held after the procedure until the surgical site is reasonably healed, for at least 7 days after the urgent surgical procedure.

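### Section 5.3.1.4 requires no ibrutinib hold for some major bleeds at platelets of 50,000/µL or more, and Table 1 sets no bleeding-free condition for restart

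*Combined protocol and SAP*

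**What the plan says.** Section 5.3.1.4 lists the toxicities that call for an ibrutinib dose change. Two entries can reach a bleed as such. One is Grade 3 thrombocytopenia (below 50,000/µL) "in the presence of clinically significant bleeding events". The other is the general line, "Any other Grade 4 or unmanageable Grade 3 toxicity". Grade 4 thrombocytopenia (below 25,000/µL) triggers action whether or not there is bleeding.

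Table 1 then applies. At the first occurrence, ibrutinib is withheld until the event is Grade 1 or lower or back to baseline, after which the subject "may restart at original dose level". Later occurrences step the dose down, and the fourth stops the drug. Hemorrhage has no separate row.

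Section 11.4.6.1 defines major hemorrhage as a bleed of Grade 3 or higher, a serious bleed of any grade, or a CNS bleed of any grade. It asks that a bleed needing red-cell transfusion be graded 3 or higher. The consequence it attaches is reporting as an event of special interest.

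Section 6.2.4 concerns anticoagulants. Where therapeutic anticoagulation is indicated, ibrutinib is held and may resume only once the subject is stable and shows no sign of bleeding.

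**The concern.** Section 1.5.2 reports hemorrhage on ibrutinib both with and without thrombocytopenia, and names gastrointestinal bleeding, intracranial hemorrhage and hematuria among the major events. The one bleeding-specific trigger in 5.3.1.4 is nevertheless tied to a low platelet count. Inclusion criterion 1 requires platelets above 50,000/µL, so every subject enters the trial in the range where that trigger does not apply.

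Followed as written, the section lets daily ibrutinib continue through some bleeds that the protocol itself calls major, unless the investigator decides otherwise. Where a hold is triggered, the written restart condition can be met while a Grade 1 bleed is still present. What is at stake is subject safety. A CNS bleed can be irreversible, and the day-to-day dosing decision comes well before the 15-day reporting limit in 11.4.6 or the monthly committee review in 12.4.

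**Working it through.** No arithmetic applies. The check takes each kind of bleed through the written triggers, then looks for a hold or restart rule elsewhere in the document.

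**Step 1: triggers.** Assume platelets of 50,000/µL or more, no antiplatelet agent, no therapeutic anticoagulation and no procedure covered by section 6.4.

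| Bleed | Major hemorrhage per 11.4.6.1 | Platelet triggers | General line | Action required by 5.3.1.4 |
|---|---|---|---|---|
| CNS, Grade 1-2 | Yes | Not met | Not met | None |
| Any site, Grade 3, judged manageable | Yes | Not met | Not met | None |
| Any site, Grade 3, unmanageable | Yes | Not met | Met | Withhold; Table 1 |
| Any site, Grade 4 | Yes | Not met | Met | Withhold; Table 1 |

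The first two rows are the gap.

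**Step 2: restart.** Table 1 asks for Grade 1 or lower, or baseline. Section 6.2.4 asks for clinical stability and no bleeding signs. A persisting Grade 1 bleed satisfies the first condition and fails the second. The written condition after an actual severe bleed is therefore weaker than the one that applies when an anticoagulant is indicated.

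**Step 3: other rules that could close the gap.**

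- Exclusion 18 carries a note to withhold ibrutinib for any bleeding event. It is worded for subjects on antiplatelet agents and gives no restart condition.
- Section 6.4 is triggered by a procedure, not by the bleed. Section 6.4.1 covers minor procedures. Section 6.4.2 applies "For any surgery or invasive procedure requiring sutures or staples for closure". Section 6.4.3 says that "ibrutinib should be held after the procedure until the surgical site is reasonably healed". A bleed managed without a procedure is outside all three.
- Section 9.2 ends treatment for unacceptable toxicity (item 1), for an adverse event that prevents further ibrutinib (item 3), by investigator decision (item 5), or after an ibrutinib hold of more than 4 weeks (item 9). Items 1, 3 and 5 rest on judgment. Item 9 limits the length of a hold that has already begun. None starts a hold or sets a restart condition for the two bleeds in the gap.
- Physician choice (3.2.1, 8.2) allows a stop but does not require one.
- A treatment-related Grade 3 or higher bleed in cycle 1 is a dose-limiting toxicity under 5.2.1. That text states no dosing action for the affected subject. The schema figure in 3.1.1 was not available, so any action shown there could not be checked.

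The search found no mandatory hold for the two bleeds, and no bleeding-free restart condition under Table 1.

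**The case against.** The strongest reply is that a competent investigator would stop ibrutinib for a CNS bleed or a transfused bleed, and that section 9.2 gives full authority to do so. The word unmanageable is undefined, so an investigator may judge any transfusion-requiring bleed unmanageable on ibrutinib and apply Table 1. What remains is narrow: adequate platelets, no antiplatelet agent, no covered procedure, a judgment of manageable, and a decision to keep dosing. This stands as a limit on how many subjects are affected. It does not supply a rule, and a second site is planned where a written rule would help consistency.

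A reader might go further and infer that Table 1 contradicts exclusion 8, which bars "History of stroke or intracranial hemorrhage within 6 months prior to enrollment", because an on-study restart can come within 4 weeks of the hold. The documents do not support that reading. Entry rules here are openly stricter than on-study rules. Child-Pugh class B is excluded at entry (item 21), yet a subject who becomes class B on study continues at 140 mg (5.3.1.5). Platelets must exceed 50,000/µL at entry, yet Grade 3 thrombocytopenia without bleeding triggers no change. The two intervals also measure different things: one is time since a bleed, the other the longest permitted hold. Their ratio says nothing about harm.

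A reader might also infer that the protocol directs full-dose rechallenge after a severe bleed. It does not. Table 1 permits restart and does not require it.

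**Conclusion.** The point holds as a patient-safety gap that is cheap to close. At platelets of 50,000/µL or more and without an antiplatelet agent, 5.3.1.4 requires no hold for a Grade 1-2 CNS bleed or a Grade 3 bleed judged manageable. Where Table 1 does apply, it lacks the stability and no-bleeding condition that the protocol already uses in 6.2.4.

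The number of subjects affected is probably small among the 30 planned. It cannot be estimated, because the documents give no hemorrhage rate by grade, platelet count or antiplatelet use. The conclusion rests on a literal reading of the trigger list, on the assumptions in step 1, and on the unseen schema containing no bleeding rule.

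It does not follow that permanent discontinuation after a CNS bleed is required by the protocol's own logic. That is a clinical choice for the sponsor.

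**What to change.** Add one trigger to 5.3.1.4: for any major hemorrhage as defined in 11.4.6.1, regardless of platelet count or manageability, withhold ibrutinib; restart under Table 1 only when the event is Grade 1 or lower or baseline and the subject is clinically stable with no signs of bleeding. Add a cross-reference from 11.4.6.1. Because that definition includes serious bleeds of any grade, the trigger would cover those as well.

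The cost is one line and one cross-reference, with no new assessments. There are three downsides to accept knowingly.

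- A few subjects will have ibrutinib held who might otherwise have continued. Each such hold would count as a Table 1 occurrence, and after a reduction "dose escalation of ibrutinib to a previous higher dose is NOT allowed".
- Section 9.2 item 9 adds a consequence for the partner drug: "If Ibrutinib therapy is held for greater than 4 weeks, then the subject must discontinue from the nivolumab as well". A long hold for bleeding would therefore also end nivolumab. Whether that is intended is a separate question, and this change leaves it alone.
- In cycle 1, a hold of more than 7 days (28 − 21) would leave less than the 3 weeks of ibrutinib that 5.2.1 requires for a subject to be evaluable for dose-limiting toxicity.
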